10.2.6 Reporting Pregnancy and Lactation to the Sponsor

Although pregnancy and lactation are not considered AEs, it is the responsibility of Investigators or their designees to report any pregnancy or lactation in a subject (spontaneously reported to them), that occurs during the study or within 120 days of completing the study, or 30 days following cessation of treatment if the subject initiates new anticancer therapy, whichever is earlier. All subjects who become pregnant must be

followed to the completion/termination of the pregnancy. Pregnancy outcomes of spontaneous abortion, missed abortion, benign hydatidiform mole, blighted ovum, fetal death, intrauterine death, miscarriage and stillbirth must be reported as an SAE (Important Medical Events). If the pregnancy continues to term, the outcome (health of infant) must also be reported.

Such events must be reported within 24 hours of awareness to Syneos Health Clinical Pharmacovigilance (Attn: Syneos SAE Reporting; [contact] or email: [contact]).

10.3 Data Monitoring Committee

Details on safety monitoring, modifying or stopping the study early are found in the [Data Monitoring Committee Charter](#). In general, consideration will be given to modifying the treatment or stopping the study early based on the reports of the DMC if:

1. the futility boundary is crossed in the planned, formal interim analysis (See [Section 11.3](#))
2. a clearly more effective therapy becomes available
3. the toxicity associated with ADXS11-001 treatment appears to outweigh the potential benefit to the subjects

The toxicity would be considered excessive if in the ADXS11-001 arm there is a significantly higher than expected rate of life-threatening (Grade 4) AEs. The DMC will formally evaluate unblinded study reports which will provide detailed tabulations of all AEs by grade and treatment group on a regular, ongoing basis in accordance with the schedule as defined in the DMC Charter.

11.1 Sample Size Considerations

For a study involving a sample of subjects with the same distribution of stage as listed in (Table 9), the estimated probability of surviving disease-free for at least 4 years is approximately 50%. Thereafter, the probability of recurring or dying increases very slowly (2-3% per year). This study will be considered sufficiently mature for a final analysis when there are at least 184 subjects reported as having experienced either recurrence of their cancer or death due to any cause. This number of events provides 85% power for detecting a treatment hazard ratio (HR) of 0.620. The type I error will be set to 0.025 (accounting for interim analysis) for a one-tail test of the null hypothesis (HR=1) using stratified logrank procedure. A treatment hazard ratio of 0.620 is comparable to increasing the expected proportion alive and disease-free for at least 4 years from 0.500 to 0.651.

Table 9 Summary of Study Parameters and Targeted Sample Size

Design Parameter	
Type I error (1-sided)	0.025
Statistical power	0.85
Treatment: Reference allocation ratio	2:1
Interim analysis *	50% IT
Hazard ratio H_A	0.620
Percent increase in DFS at 4 yrs. H_A	0.151
Number of DFS events required**	184
Target accrual (N of subjects)***	450
Accrual duration****	55 months
Post-accrual follow-up duration****	20 months

*An interim analysis of safety and efficacy planned at 50% of the information time (IT)

**East version 5.4, H_A is the alternative hypothesis for power calculations.

***Assumes cumulative probability of recurring or dying on the reference treatment during the first 4 years is approximately 50%, and thereafter this probability does not increase. See Note on Target Accrual (below).

****The estimated duration of accrual and post-accrual follow-up depend on the expected average accrual rate and the number of investigative sites participating in the study. It is estimated that ~ 450 subjects will be enrolled in 55 months.

A Note on Target Accrual: The statistical power of this study is a function of the expected number of subjects experiencing either recurrence or death observed in each treatment group at the time of final analysis. The anticipated DFS event rate in this population is relatively high during the first 4 years of enrollment but declines considerably thereafter. Specifically, the cumulative probability of recurrence or death with the first 4 years is expected to be at least 50% (see Figure 4). However, for those who have not recurred during the first 4 years, the cumulative probability of recurrence or death during the subsequent 4 years is expected to be less than 10%. It is anticipated that about 30-40% will not experience a recurrence of

their cancer within their lifetime. The targeted accrual for this study is based on the expected (mean) number of recurrences or deaths that will be observed under the alternative hypothesis after following each subject for at least 4 years. However, the number of subjects experiencing either recurrence or death within 4 years of for a particular study is actually a random number. By chance alone, the actual number of DFS events in this study could be less than expected. Moreover, it is possible for more than planned low-risk subjects could be enrolled. Therefore, it is prudent to enroll slightly more subjects than the minimum. Assuming that there are no subjects who recur after the first 4-years of follow-up, as was done for this study to determine the target accrual, provides some protection for underestimating the actual proportion of subjects recurring in the study sample. It is worth noting that this study will include criteria, which were not used in GOG-219, to clinically determine node involvement (e.g., minimum size of nodes) that are intended to reduce the frequency of false-positives. Therefore, the DFS event rate observed in this study could be slightly higher than predicted by the historical data from GOG-219 (see [Section 11.2.7](#)).

11.2.1 Study Design

This is a 2-arm, placebo-controlled, randomized (2:1 ADXS11-001/placebo), Phase 3 clinical study. The treatment for each enrolled subject will consist of either:

- Placebo (P)
- ADXS11-001 (E)

The general objective of this study is to evaluate the relative efficacy and safety of adding ADXS11-001 in the adjuvant setting following CCRT with curative intent for the treatment of women with HRLACC.

11.2.2 Definition of Study Populations for Analyses

The primary analysis population for the primary efficacy endpoints will be based upon the intention to treat (ITT) principle population. The ITT population includes all subjects enrolled into this study regardless of their eligibility or compliance with their assigned treatment. Secondary efficacy endpoints will be reported for the ITT population. Analyses of adverse events will include all subjects enrolled into this study who initiated their assigned study treatment.

11.2.3 Measures of Efficacy and Safety

The principal observations for evaluating the therapeutic efficacy and safety of the study regimens are:

1. Primary efficacy endpoint: DFS
2. Secondary efficacy endpoint: OS

Safety endpoints: frequency and severity of related AEs as defined by CTCAE v 4.03, changes in physical examinations, vital signs measurements, and clinical laboratory evaluations. An external DMC will evaluate and analyze accrued subject data periodically throughout the study.

For the analyses of the primary endpoint, the DFS duration for each subject will be assessed from the date of randomization to the date of first recurrence as determined by independent radiology review or death (due to any cause). For those subjects who have not recurred or died, the duration at risk of recurrence will be calculated up to the date of the subject's last disease assessment.

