Criteria for Evaluation	
Efficacy: DFS evaluated using progression-based evaluation methodology every 3 months, beginning 3 months after the first dose for the first 2 years and then every 6 months for the next 4 years for a total of 6 years; and OS

	
Safety: assessed at every visit by comparing treatment-related adverse events (AEs); changes in physical examinations, vital signs measurements, clinical laboratory evaluations during the treatment period, and Lm surveillance blood cultures and listeremia-related adverse events (AEs) during the follow-up period; an independent Data Monitoring Committee (DMC) will evaluate and analyze accrued subject data periodically throughout the study treatment period.

Statistical Considerations	
Statistical Analysis Plan provided as a separate document, is adjusted to assess data collected up to the time of early study termination rather than post 184 events previously planned for full maturity of the study.

Figure 1 Study Schema

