1.2 Secondary Objectives

- To determine and compare the frequency and severity of adverse events (AEs) as assessed by National Cancer Institute (NCI) Common Terminology Criteria for Adverse Events (CTCAE) version 4.03 for the regimens administered on this study.

- To evaluate the overall survival (OS) of ADXS11-001 administered in the adjuvant setting following definitive therapy of CCRT in subjects with HRLACC.

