2.2.2 Safety Endpoints

[figure not shown]
The safety objective of this study is to determine and compare the frequency and severity of AEs as assessed by NCI CTCAE v 4.03 for the regimens administered on this study.

The safety of ADXS11-001 administration will be assessed according to the NCI CTCAE v 4.03 criteria which will be used to define the grades and levels of toxicity. These criteria will be applied to:

- Observation of the infusion site for swelling, irritation, immune reaction or other abnormalities
- Changes from baseline in physical examination findings and vital signs
- Changes from baseline in laboratory parameters (hematology, serum chemistry and urinalysis)
- Evidence of allergic and constitutional symptoms
- Other adverse events

Safety evaluations will be performed throughout the study. All subjects who received at least 1 dose of study treatment (placebo or ADXS11-001) will be evaluated for safety. The AE grade, attribution to drug, date of onset, duration of the event, outcome, impact on study treatment, any concomitant medications, procedures and/or therapies administered will be recorded.

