5.2.3.1 Pretreatment Prophylaxis Regimen

Mild to moderate cytokine release symptoms (e.g., fever, chills, rigors, fatigue, headache, nausea, vomiting, tachycardia, shortness of breath, hypotension and rash) are commonly seen and typically occur 2-4 hours after ADXS11-001 infusion and often resolve within 12-24 hours. Prophylactic medications are intended to reduce the inflammatory response and minimize the occurrence of post-treatment symptoms. Therefore, it is strongly recommended that subjects receive the following pretreatment prophylaxis regimen:

IV Fluid Hydration:

- Normal saline (NOTE: A recommended fluid amount is 500 mL administered IV over approximately one hour but investigator discretion should be used to determine an individual subject's need based on her medical condition. Appropriate hydration has been determined to be a key component in helping to minimize post-treatment symptoms related to an immune-mediated response.)

[figure not shown]
Premedication Regimen:

- Antihistamine - PO or IV (e.g., diphenhydramine 25 mg or equivalent) [REDACTED] prior to the procedure, once
- NSAIDs - PO (e.g., naproxen 220 mg or ibuprofen 400 mg) [REDACTED] prior to the procedure, once
 - NOTE: Acetaminophen is prohibited for prophylaxis because it does not have anti-inflammatory properties required to assist in reducing adverse events associated with ADXS11-001 administration. When naproxen and ibuprofen are contraindicated an alternative anti-inflammatory should be used. Acetaminophen may be used for supportive care measures. Sponsor consultation is recommended.
- Antiemetic - PO or IV (e.g., promethazine or ondansetron) [REDACTED] prior to the procedure, once
- Histamine H2-receptor antagonist - PO or IV (e.g., famotidine 20 mg or equivalent) [REDACTED] prior to the procedure, once

IV fluids and pretreatment medications should be given on the day of dosing and completed at least [REDACTED] prior to the start of the assigned study treatment infusion. Do not substitute acetaminophen for the selected NSAID for prophylactic treatment since acetaminophen does not have similar anti-inflammatory properties that could ameliorate symptoms related to an immune-mediated response.

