10.2.1 Evaluating Adverse Events

An Investigator who is a qualified physician will evaluate all AEs according to the NCI CTCAE v 4.03. Any AE that changes CTCAE grade over the course of a given episode will have each change of grade recorded on the AE eCRF. In these cases, when the intensity of an AE changes over time for a reporting period (e.g., between visits) each change in intensity will be reported as an adverse event until the AE resolves. For example, 2 separate AEs will be reported if a subject experiences Grade 1 diarrhea for 3 days, meeting the definition of an AE, and then after 3 days the AE increases to a Grade 3 intensity that lasts for 2 days and then resolves. The Grade 1 event will be reported as an AE with a start date equal to the day the event met the AE definition and a stop date equal to the day that the event increased in intensity from Grade 1 to Grade 3. The Grade 3 event will also be reported as an AE with the start date equal to the day the event changed in intensity from Grade 1 to Grade 3 and a stop date on the day that the event changed intensity again or resolved. For analysis purposes, this will be considered one AE for this subject and the maximum intensity will be recorded.

When possible, AEs should be described in terms of a change in the baseline status or with a diagnosis or summary term rather than as individual symptoms.

Criteria for Determining AE Severity: The descriptions and grading scales found in the revised NCI CTCAE v 4.03 will be utilized for AE reporting.

Criteria for Determining AE Causality: The following attribution categories must be used in assessing the relationship between the AE and the study treatment: If the Investigator does not know whether or not the investigational agent caused the event, then the event will be handled as “related to investigational agent.”

RELATIONSHIP	ATTRIBUTION	DESCRIPTION
Unrelated to investigational agent/intervention	Unrelated	The AE is clearly NOT related to the study treatment
	Unlikely	The AE is doubtfully related to the study treatment
Related to investigational agent/intervention	Possible	The AE may be related to the study treatment
	Probable	The AE is likely related to the study treatment
	Definite	The AE is clearly related to the study treatment

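### The safety objective is to compare all AEs between regimens, but the AE endpoint counts only related AEs, and whether oral-antibiotic AEs count as related is undefined

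*Combined protocol and SAP*

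**What the plan says.** Two places set the aim without reference to causality. Section 1.2 reads "To determine and compare the frequency and severity of adverse events (AEs", and Section 2.2.2 gives the safety objective as to "determine and compare the frequency and severity of AEs as assessed by NCI CTCAE v 4.03 for the regimens administered on this study".

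Two places narrow it. The synopsis (Criteria for Evaluation) has safety "assessed at every visit by comparing treatment-related adverse events (AEs". Section 11.2.3 has "Safety endpoints: frequency and severity of related AEs as defined by CTCAE v 4.03", and the same sentence goes on to list changes in examinations, vital signs and laboratory results. In that sentence the word related qualifies the AEs; the examination, vital-sign and laboratory components are not qualified.

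Section 10.2.1 has the investigator assign one of five causality categories relative to study treatment. Possible, probable and definite count as related; unlikely and unrelated do not. "If the Investigator does not know whether or not the investigational agent caused the event", the event is handled as related.

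Study treatment has two meanings. Section 10.1 glosses it as ADXS11-001 or placebo. Table 4, which carries the title Study Treatment, also lists trimethoprim/sulfamethoxazole for Arm B and a matching placebo for Arm A.

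**The concern.** In a randomized placebo-controlled trial, comparing all treatment-emergent AEs by arm is protected by randomization. Comparing only those AEs that an investigator judged related is not, because the judgement is made after randomization and can differ by arm if the investigator suspects the assignment.

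The protocol gives reasons to think suspicion is possible. Cytokine release symptoms "are commonly seen and typically occur 2-4 hours after ADXS11-001 infusion" (Section 5.2.3.1), and subjects stay in clinic for at least 4 hours after dosing (Section 5.2.3.5). Section 6.2.3 reports Grade 3 and 4 hypotension in about 7% of subjects given ADXS11-001. Subjects who become sensitive to trimethoprim/sulfamethoxazole are formally unblinded (Sections 6.2.5.1, 6.2.6 and 7.2.1.9).

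The objective also concerns regimens. By Table 4 the Arm B regimen includes an active oral antibiotic. If attribution is made to ADXS11-001 alone, an event that the investigator ascribes to the antibiotic could fall outside the AE endpoint although it belongs to the regimen under comparison. With 110 of 450 planned subjects randomized (Section 11), safety is a larger share of what the trial can report.

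**Working it through.** The plan gives no figure on this point, so there is none to reproduce. The check is a comparison of text, followed by an illustration of scale under stated assumptions.

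**1. Objective against endpoint.**

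| Place | AEs to be compared |
|---|---|
| Section 1.2 | all |
| Section 2.2.2 | all, by regimen |
| Synopsis, Criteria for Evaluation | treatment-related |
| Section 11.2.3 | related |

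The narrowing appears twice, once in the section that defines the endpoints, so it is unlikely to be a slip in a single sentence.

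**2. Does an antibiotic-caused AE count as related?** Under Section 10.1, no: study treatment is ADXS11-001 or placebo. Under Table 4, yes: the antibiotic and its placebo are listed as study treatment. Section 10.2.1 does not decide between them, since it refers to study treatment in one place and to the investigational agent in another. The handling is undefined.

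**3. Antibiotic exposure by arm.** Sections 6.2.5.1 and 6.2.6 give a 7-day course after each of the first seven doses and a 3-week course after the eighth. A subject completing all eight doses has 7 × 7 + 21 = 70 days, active in Arm B and matching placebo in Arm A by Table 4. Subjects who stop early have fewer. Section 2.1.7.1, footnote 10 of the Schedule of Events and part (2) of Section 7.2.1.9 say that all subjects receive antibiotics without mentioning placebo. These passages and Table 4 must be reconciled.

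**4. What differential attribution could do (assumed rates).** Inputs from the plan: 110 subjects at 2:1, so 110/3 ≈ 37 in Arm A and 220/3 ≈ 73 in Arm B. Assumed: the same true proportion *p* of subjects with an AE in both arms, and attribution shares sA and sB. Observed related-AE rates are p·sA and p·sB.

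The chance of a nominal two-sided p < 0.05 in the direction B > A is Φ[(d − 1.96·se0)/se1], where d is the difference, se0 the pooled and se1 the unpooled standard error. For p = 0.5, sA = 0.3, sB = 0.7:

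- rates are 0.15 and 0.35, so d = 0.20
- pooled rate = (37 × 0.15 + 73 × 0.35)/110 = 0.283
- se0 = √[0.283 × 0.717 × (1/37 + 1/73)] = 0.091
- se1 = √[0.15 × 0.85/37 + 0.35 × 0.65/73] = 0.081
- Φ[(0.20 − 0.178)/0.081] = Φ(0.27) = 0.61

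| p | sA, sB | Related A, B | Chance of nominal p < 0.05 |
|---|---|---|---|
| 0.5 | equal (0.5, 0.5) | 25%, 25% | 2.5% |
| 0.5 | 0.4, 0.6 | 20%, 30% | 19% |
| 0.5 | 0.3, 0.7 | 15%, 35% | 61% |
| 0.5 | 0.2, 0.8 | 10%, 40% | 94% |
| 0.3 | 0.3, 0.7 | 9%, 21% | 34% |
| 0.7 | 0.3, 0.7 | 21%, 49% | 84% |

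The true difference is zero in every row. The plan specifies no AE test; the last column only conveys scale.

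**5. What the antibiotic ambiguity could do (assumed rates).** If antibiotic-caused AEs occurred in 3% to 10% of Arm B and were judged not related, 73 × 0.03 = 2.2 to 73 × 0.10 = 7.3 subjects, about 2 to 7, would have such events left out of the AE endpoint.

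**The case against.** The strongest case on the other side is that little is lost. AEs are recorded whatever their cause (Section 10.2). The DMC receives unblinded tabulations of every AE by grade and arm (Section 10.3). Section 11.2.2 describes AE analyses without the word related. The available text specifies no AE hypothesis test. Section 11.2 is a summary of a separate SAP that may already tabulate all treatment-emergent AEs. These points stand, and they limit the consequence. They do not remove the mismatch: DMC tables serve monitoring, Section 11.2.2 defines a population, and Section 11.2.3 is where the endpoint is defined.

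A reader might infer three stronger things, none of which the documents support.

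- *That antibiotic toxicity is omitted from the endpoint.* Table 4 counts the antibiotic as study treatment, and an event of unknown cause defaults to related. Rash is also among the listed cytokine symptoms, so an uncertain rash would probably be counted. Undefined is the accurate word.
- *That the whole safety comparison rests on attribution.* Laboratory, vital-sign and examination changes are unfiltered, so a cytopenia would still appear in the laboratory results.
- *That investigators are in effect unblinded.* This is a reasonable inference for some subjects, but the documents neither state nor measure it.

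Nor is antibiotic use in Arm A firmly nil. Besides the passages that omit placebo, Section 6.2.5.1 lets oral antibiotics be considered for persistent fever without limiting this to one arm.

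**Conclusion.** The inconsistency holds: the objective covers all AEs, while the AE component of the safety endpoint, in the synopsis and Section 11.2.3, covers only related AEs. Followed as written, the plan would compare arms on events selected by investigator judgement in a setting where some assignments can be guessed. Whether antibiotic-caused AEs fall inside that selection is undefined.

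The size of any bias is unknown. The 15% versus 35% example and the 2 to 7 subjects rest on assumed rates, and the former also assumes that attribution differs systematically by arm. The conclusion about the endpoint wording needs none of these assumptions. It is limited to the protocol text, because the full SAP could not be checked. This should be corrected, but it does not undermine the safety data that are collected.

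**What to change.** - In Section 11.2.3 and the synopsis, define the AE endpoint as the frequency and maximum grade of all treatment-emergent AEs and SAEs by arm, regardless of attribution. State the time window; Section 10.2 already records all AEs to 30 days after the last dose.
- Keep related AEs as a supportive table.
- State in Sections 10.1 and 10.2.1 whether attribution covers the oral antibiotic and its placebo.
- Reconcile Section 2.1.7.1, footnote 10 of the Schedule of Events and Section 7.2.1.9 with Table 4 on who receives active antibiotic and who receives placebo.
- If the separate SAP already tabulates all treatment-emergent AEs by arm, align the synopsis and Section 11.2.3 to it.

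The cost is wording changes and at most one extra table set. No new data are needed.

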8.2 Determination of Disease Recurrence

The following criteria define the methodology which can be used to define disease recurrence.

- Clinical deterioration alone **cannot** be utilized as the sole determinant of recurrence and needs to be confirmed by either imaging or confirmatory biopsy.
- Results from the physical and/or pelvic exam, including cytologic assessment of a PAP smear, **cannot** be utilized as the sole determinant of recurrence and need to be confirmed by either radiographic imaging or confirmatory biopsy/fine needle aspirate of a suspected lesion.
- Results from biopsy/FNA of a suspected lesion can be utilized as the sole determinant of recurrence. However, results from radiographic imaging as determined by independent radiology review can only be utilized as the sole determinant of recurrence in the event that a tissue confirmation is not medically feasible in the opinion of the investigator. In cases where radiologic imaging confirms disease recurrence and a biopsy/FNA was obtained of the tumor being evaluated by imaging which is negative, then the subject will be considered to have disease recurrence. Histopathologic or cytologic assessment of tumor can occur by local lab.

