8.2.1 Definition of Recurrence

The determination of recurrence must occur by definitive pathologic tissue confirmation (e.g., biopsy/fine needle aspirate). However, in those cases where it is not medically feasible to obtain a tissue sample then radiographic evidence, when confirmed by independent radiology review, will be used to determine recurrence.

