8.2.1.2 Types of Radiographic Assessments

Three types of radiologic assessments will be performed in this study.

- (1) Site Reads – These are performed on all subjects at baseline and follow-up time points. The site reads are used primarily for subject management.
- (2) Confirmation of Recurrence Reads – These reads are performed by a small, limited pool of independent radiologists trained on the criteria and with expertise in radiologic evaluation of this subject group. If the results of the Site Read demonstrate recurrent disease (RD,) the images are electronically transmitted to the imaging core lab and within 72 hours from receipt the

results of an independent Confirmation of Recurrence (COR) will be transmitted to the site. The role of this reader is very targeted – to ONLY confirm or not confirm disease recurrence. The purpose of this assessment is to prevent subjects from being removed too early before true recurrence has actually occurred.

- (3) Blinded Independent Read – Each subject will be separately evaluated by two readers for the RD parameters. When the two readers disagree on the presence or date of recurrence, a third expert reviewer (the Adjudicator) will review all results and select to agree with either reader A or B. The purpose of this read is to confirm RD. A separate radiology charter provides detailed information on all aspects of the radiographic assessments to be utilized for this protocol including adjudication. An independent radiology review will be conducted to confirm recurrence for all subjects. The independent radiology review will both an independent efficacy review and an independent review of COR.

In summary:

- The objective of the independent efficacy review is to prospectively determine when a subject enrolled in the study has developed a new tumor(s) that qualifies them for the recurrence determination. Expert and trained independent efficacy reviewers will interpret the images for the radiology review with no clinical information available. The independent efficacy review will provide the Sponsor with an assessment of the Time Point Response (TPR; NOTE: TPR will be limited to Recurrent Disease, [RD], non-RD, or Unable to Evaluate [UE] only; refer to [Section 8.2.1.4](#)) and the Date of Recurrence (if applicable) for each subject enrolled in the study.

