8.2.1.4 Radiographic Assessment of Time Point Response

[figure not shown]
Radiographic assessments at each time point will be based on the presence or absence of new lesions. The time point assessment will be classified as either non-RD, RD or UE. This TPR is assessed with reference to Baseline for the evaluation of RD. The TPR for each time point will still be determined even in cases where the prior time point demonstrates RD. In addition, if an identified new lesion subsequently becomes UE it will continue to be considered present and classified as a RD.

[Table 8](#) shows “Imaging Time Point Assignment of Response Including Biopsy Information.” In situations where a biopsy result is negative for tumor, but results from imaging demonstrate disease recurrence then the final determination of RD will be based on the imaging results. In situations where a biopsy result is positive for tumor, but results from imaging do not demonstrate disease recurrence, then the final determination of RD will be based on the biopsy results.

Table 8 Imaging Time Point Assignment of Response Including Biopsy Information

Time Point Imaging Response	Biopsy Result¹	Final Timepoint Imaging Response
RD	Not medically feasible	RD
	Positive for tumor	RD
	Negative for tumor	RD
UE	Not medically feasible	UE
	Positive for tumor	RD ¹
	Negative for tumor	UE
Non-RD	Not medically feasible	Non-RD
	Positive for tumor	RD ¹
	Negative for tumor	Non-RD

¹A biopsy result, which is positive for disease, dictates a final timepoint response of recurrent disease irrespective of the imaging response.

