11.2.6 Analytic Procedures for the Testing Hypothesis: Hp:E,DFS

The logrank procedure will be used to evaluate the primary study hypothesis. The logrank calculation will be stratified by 2014-FIGO tumor stage (I or II vs III or IV) system, region (US vs Rest of World), para-aortic node metastases (yes vs no/unknown). The analysis of DFS will consider all deaths as events, regardless of the cause of death. The impact of the

other potential prognostic/predictive factors will be explored in multivariate and/or subgroup analyses and will include, but not necessarily limited to, prior brachytherapy and radiation field at baseline. A sensitivity analysis will be performed to evaluate subjects who were determined to meet the criteria for recurrence based on radiographic imaging, but the results from biopsy were negative. The SAP will provide details for the sensitivity/supportive analyses which will be performed.

For the primary analysis, subjects will be grouped according to their randomly assigned treatment and subjects will be included in the analysis, regardless of their compliance with their assigned treatment plan. The primary analyses will use the duration of DFS as it is determined by the Independent Radiology Reviewer.

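### Sections 8 and 11 conflict on whether a biopsy-proven recurrence with a non-RD or UE independent read is a primary DFS event

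*Combined protocol and SAP*

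**What the plan says.** **Section 8 gives tissue priority.** Section 8.2: "Results from biopsy/FNA of a suspected lesion can be utilized as the sole determinant of recurrence". The same bullet lets independently reviewed imaging stand alone only where tissue cannot feasibly be obtained. Section 8.2.1: "The determination of recurrence must occur by definitive pathologic tissue confirmation (e.g., biopsy/fine needle aspirate"). Section 8.2.1.4 takes up the discordant case directly. Where the biopsy is positive and imaging does not show recurrence, "then the final determination of RD will be based on the biopsy results". The footnote to Table 8 adds that a "biopsy result, which is positive for disease, dictates a final timepoint response of recurrent disease irrespective of the imaging response".

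**Section 11 gives radiology priority.** Section 11.2.3 runs DFS "from the date of randomization to the date of first recurrence as determined by independent radiology review or death (due to any cause"). Section 11.2.6: "The primary analyses will use the duration of DFS as it is determined by the Independent Radiology Reviewer". Neither section names biopsy or FNA as an event source. On censoring, Section 11.2.3 follows subjects with neither recurrence nor death to their last disease assessment.

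**The readers.** Under Section 8.2.1.2 the independent efficacy reviewers "interpret the images for the radiology review with no clinical information available".

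**Sensitivity analysis.** Section 11.2.6 names one analysis of discordance, for subjects with recurrence on imaging and a negative biopsy. It leaves further detail to the SAP, which Section 11.2 describes as a separate document.

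**The concern.** The primary endpoint has two readings. An analyst working from Table 8 counts a tissue-proven recurrence as an event. An analyst working from 11.2.3 and 11.2.6 does not, unless the independent readers also call recurrence or the subject dies. The two could report different event counts and dates from the same data.

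On the second reading, censoring is triggered by proven recurrence and is therefore informative: the DFS curve in each arm would sit too high. Only 110 of the planned 450 subjects are analysed, so each event carries more weight than the design intended.

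**Working it through.** **1. The plan's own figures.** Section 11.1 gives HR 0.620, one-sided alpha 0.025, power 0.85, 2:1 allocation and 4-year placebo DFS of 0.50.
- 4-year DFS under the alternative: 0.50^0.62 = 0.651, as stated.
- Events, fixed design (Schoenfeld): (1.960 + 1.036)^2 / [(2/9) x (ln 0.62)^2] = 8.978 / (0.2222 x 0.2285) = 176.8, so 177.
- Adding O'Brien-Fleming-like alpha spending and non-binding beta spending at 50% information gives 183.8, so 184, with power 0.850.

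The 184 reproduces. This point does not dispute it.

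**2. The two rules side by side.**

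| Independent read | Biopsy/FNA | Table 8 | Section 11, literal | In the named sensitivity analysis? |
|---|---|---|---|---|
| RD | positive or not feasible | RD | event | not needed |
| RD | negative | RD | event | yes |
| Non-RD | positive | RD | no event yet | no |
| UE | positive | RD | no event yet | no |
| Non-RD or UE | negative or not feasible | unchanged | no event | not needed |

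The rules part only in the third and fourth rows, and the sensitivity analysis addresses only the second.

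**3. Can the event be captured later?** Partly.
- For: death from any cause counts. Section 7.2.6.1.1 lists tumor imaging at the End of Study visit when recurrence ends treatment. Section 7.2.5.2.1 sends unscheduled scans to the central laboratory. Section 8.2.1.4 still assigns a response at time points after RD.
- Against: scheduled imaging is for subjects without documented recurrence (Schedule of Events, footnotes 3 and 20; Section 7.2.6.1.2). After recurrence, footnote 23 provides telephone contact for listeremia symptoms. Section 11 ends efficacy evaluations at termination, 31 July 2019.

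**4. The date.** Section 8.2.1.2.1 dates recurrence at the first time point with RD. Section 8.2.1.2.2 dates a time point by its first radiographic evaluation. Neither gives a date for recurrence proven by tissue before, or without, a positive scan. A discordant subject whose scan later turns positive is thus also affected.

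**5. Size.** The documents do not give the discordant share f; 5-20% is an assumption. If a fraction f of the DFS hazard is treated as censored and never captured later, apparent 4-year placebo DFS = 0.50^(1-f).

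| f | 0.50^(1-f) |
|---|---|
| 5% | 0.518 |
| 10% | 0.536 |
| 15% | 0.555 |
| 20% | 0.574 |

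These are upper bounds for each f, because any later death or independent RD read restores an event. Events counted are (1-f) times the total. The documents do not give the number of events among the 110 subjects; for every 20 DFS events, 5-20% is 1 to 4.

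**6. Hazard ratio.** If f is equal in both arms and nothing is captured later, the counted hazards are (1-f)h1 and (1-f)h0, and their ratio is unchanged. A bias requires f, or later capture, to differ by arm. The documents give no information on either.

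**The case against.** The best counter-argument is a cross-reference. Section 8.2.1.2 says that the independent efficacy review supplies the time point response and points to Section 8.2.1.4. Table 8 in that section folds biopsy into a final imaging response. On this view the readers see images only, local pathology is merged afterwards, and the discordant case is an event. That reading is possible. It does not settle the matter, because no passage says who does the merging or that 11.2.3 and 11.2.6 use the merged result.

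A reader might go further and infer that the primary analysis definitely censors these subjects. The documents do not say so: it follows only from reading Section 11 literally, and the cross-reference allows the other reading. A reader might also infer that the event can never be recovered; death, End of Study imaging and unscheduled scans can recover some. Nor can one infer a bias in the treatment comparison. The trial is double-blind, the rule applies to both arms, and no direction can be derived.

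Two further objections stand. The full SAP and the imaging charter were not available and may state the rule, although the protocol text would still need to be reconciled. And an endpoint based on blinded radiology, with biopsy added in a sensitivity analysis, is a coherent design. It is not, however, the one that Section 8 describes.

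**Conclusion.** The conflict holds and concerns the primary endpoint: Section 8 calls the case proven recurrence, while Section 11, read literally, leaves it out or dates it late. The named sensitivity analysis does not cover it. The consequence is conditional on that literal reading and on neither death nor an independent RD read following. The 0.52-0.57 range rests on the assumed 5-20% share and no later capture, and is on the 4-year planning scale, which the terminated trial will not reach in full. What is established is that the event rule is ambiguous; the effect on the trial's result is not.

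**What to change.** In 11.2.3 and 11.2.6, state one event rule and one date, consistent with Table 8: the earliest of (a) RD by independent radiology review, (b) positive biopsy or FNA, dated at tissue collection, and (c) death from any cause. Say who combines local pathology with the independent read. Report DFS by independent radiology or death as a sensitivity analysis, beside the one already planned for imaging-positive, biopsy-negative subjects, and give the number of discordant subjects by arm. Bring the full SAP into line if it does not already say this, without sight of treatment allocation.

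The cost is wording and one extra analysis; local pathology already determines recurrence under Section 8, so no new assessment is needed. The small downside is that the decision to biopsy and the pathology read are local. The radiology-or-death analysis shows how far the result depends on them.
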